**6.0 Data and Specimen Banking: N/A**

**7.0 Sharing of Results with Participants**

**7.1** No results will be shared with study participants or others.

**8.0 Study Duration**

- We anticipate that the duration for an individual subject's participation in the study would be approximately 32 weeks.
- We anticipate it will take two (2) years to enroll all study participants.
- We anticipate it will take three (3) years from the study start date to complete all study procedures and data analysis.

**9.0 Study Population**

**9.1** Inclusion Criteria: (1) Male or female kidney transplant recipient; (2) 18 years of age and above; (3) receiving a kidney transplant from a living or deceased donor; (4) if female, premenopausal and heterosexually active, must be using two forms of highly effective birth control (at least one of which must be a barrier method) which includes consistent and correct usage of established oral contraception, established intrauterine device or intrauterine system, or barrier methods of contraception: condom or occlusive cap (diaphragm or cervical/vault caps) with spermicidal foam/gel/film/cream/suppository, starting at screening and throughout the study period and for 90 days after the final study drug administration; (5) written informed consent to participate in the study.

**9.2** Exclusion Criteria: (1) younger than 18 years of age; (2) Non-native level English speaker; (3) pregnant women (4) breastfeeding women

**9.3** Screening: All patient enrollment will come from [name] patient population. Potential subjects will be identified by information contained in their medical records. The study will be introduced either in person or by mail and either the study staff or letter will thoroughly describe the requirements of the study along with the risks and benefits of participation. Study staff will be available to answer any questions from the potential participant. If the potential participant expresses interest in participating in the study, an initial study visit will be scheduled either as a stand alone visit or concurrently with a standard of care clinic visit in order to further discuss the study, address any questions, and determine the patient's final eligibility. Also see sections *12.0* (Local Recruitment Methods) and *21.0* (Consent Process) for further details.

## 10.0 Vulnerable Populations

**10.1** Vulnerable Populations: *Identify which of the following populations will be involved in this study. (You may not include members of the populations below as participants in your research unless you indicate this in your inclusion criteria above.)*

- Children
- Pregnant women/Fetuses/Neonates
- Prisoners
- Adults lacking capacity to consent and/or adults with diminished capacity to consent, including, but not limited to, those with acute medical conditions, psychiatric disorders, neurologic disorders, developmental disorders, and behavioral disorders
- Non-English speakers
- Those unable to read (illiterate)
- Employees of the researcher
- Students of the researcher
- None of the above

**10.2** *Adults lacking capacity to consent and/or adults with diminished capacity to consent:* N/A

**10.3** Additional Safeguards: N/A

## 11.0 Local Number of Participants

**11.1** Local Number of Participants to be Consented: Sample size is based on the primary endpoint (COWA). In a longitudinal neurocognitive study of patient on immune suppressant drug therapy Syrjala et al (2004) found that the mean T score for the COWA (based on a population norm set at 50, with a standard deviation SD of  $\pm 10$ ) declined by 5 units (0.5SD) from pretransplantation to 80 days posttransplantation. Since a change of 0.5SD is considered standard clinical criteria for a medium effect size, we based our calculation of the power for the COWA upon a standard deviation of the difference score between baseline and follow up of a 5-point performance decline. Therefore, a total of 65 patients will yield a probability of 80 percent that the proposed study will detect a treatment difference of 5 units in COWA at a two-sided 0.05 significance level. To account for possible dropouts, we will recruit 74 patients.

## 12.0 Local Recruitment Methods

**12.1** Recruitment Process: All patients of the transplant center are told by clinical staff and educators that they will likely be approached for research studies pre- and post-transplant. Given the number of studies and sheer volume of patients seen at the transplant center, specifics of each study are not discussed in great detail. This is largely due to the fact that the amount of time between referral to our transplant program, being waitlisted or

scheduled for transplant, and actually receiving a transplant can vary drastically between cases. Therefore, the initial approach for this study by the research team will occur post-transplant.

Eligible kidney transplant recipients will be initially contacted in person at a standard of care clinic visit or via mail. The ability to approach patients for the study either in person or via mail will allow the study team to capture all patients – those who routinely come into clinic for follow-up care and those who do not.

Subjects contacted in person will be approached by a member of the study team at a regularly scheduled clinic visit to discuss the study and provide potential subjects with a copy of the consent form to review. If the subject expresses interest in participating, either at that time or at a later time, an initial study visit will be scheduled where the subject will sign the consent form prior to any study procedures. Subjects approached via mail will be sent an IRB-approved invitation letter and copy of the IRB-approved consent form at least one to two months (maximum 36 months) after their kidney transplant surgery. A follow-up phone call will be made to the potential participant after an appropriate amount of time has passed for the letter and consent form to be delivered and reviewed. Study staff will call the potential participant, identify themselves as affiliated with the University of Minnesota, and explain to the potential participant why they are calling. The study will be introduced and the study staff will thoroughly describe the requirements of the study along with the risks and benefits of participation and answer any questions from the potential participant. If the potential participant expresses interest in participating in the study, an initial study visit will be scheduled either as a stand alone visit or concurrently with a standard of care clinic visit. The potential participant will sign the consent form at the initial study visit. This will allow plenty of time for potential subjects to review the consent form and consider the study. For additional information regarding the consent process, see section 21.0 of this protocol.

Potential participants may also choose to self-identify for this study. Our research group, the Surgery Clinical Trials Office (SurgCTO) has a website that lists our actively enrolling studies. This website is publicly available and can be reviewed by patients who want to know specifics about studies being conducted within the abdominal transplant division and contact information for the study team. Patients of the clinics are also referred to StudyFinder, which lists all active studies in which SurgCTO is participating and study team contact information.

**12.2 Source of Participants:** Participants will be recruited from the patient population SurgCTO, where the co-PI ([name]) is a practicing physician. Participants will be identified through their medical records.

**12.3 Identification of Potential Participants:** Potential subjects will be identified by information contained in their medical records. The principal investigator and the UMN research team have permissible access to the medical records as the co-PI ([name]) has a treating relationship with the patient population eligible for this study. All potential subjects are patients of the University of Minnesota Transplant Clinic and Nephrology group. Only internal patients are recruited for this study.

All members of the research team have access to EPIC. Within EPIC, researchers will first look at potential subjects' patient type to determine if they have opted out of research. If the potential subject has not opted out of research, preliminary screening will take place and a letter may be sent to the potential subject.

If the patient has opted out of research, the researcher will not look into the patient's chart, preliminary screening will not take place, and a letter will not be sent. If the patient comes to clinic for a standard of care appointment, the patient may be approached in person by the clinical team to ascertain interest in the study. If the patient expresses interest in the study, the researcher will inform the patient that they need to review the patient's medical record to determine eligibility. If the patient is eligible, the consent process will proceed.

**12.4 Recruitment Materials:** Recruitment will begin at least one to two months (maximum 36 months) after potential subjects have had a kidney transplant. A letter will be sent briefly describing the study and include contact information for the research team. The IRB-approved consent form will also be included with the letter for review. A follow-up phone call will be made to the potential participant after an appropriate amount of time has passed for the letter and consent form to be delivered and reviewed.

The recruitment letter, consent form, and script for the phone conversation will all be reviewed and approved by the IRB prior to subject recruitment. If a potential subject has a standard of care appointment at the University of Minnesota near the time he or she will be eligible for the study, study personnel may approach them in person. In that situation, the consent form will be provided to the patient to review.

**12.5 Payment:** Subjects will not incur costs as a result of participation in the study. Compensation will be \$50 for each of the four (4) study sessions (a total of \$200 if they complete all 4 visits) for their time and inconvenience. Subjects will also be eligible for up to a total of \$200 in travel expenses (reimbursed at \$0.535 per mile round trip) for the four (4) post-transplant visits (excluding the pre-BASELINE visit) during which they are scheduled to receive a battery of cognitive, motor function, and self-assessments. If a subject cannot continue or chooses to drop out of the study, their payment will be prorated for the sessions completed. Compensation will be issued from the University of Minnesota.

## 13.0 Withdrawal of Participants

**13.1** Withdrawal Circumstances: Subjects will be asked to withdraw from the study if the treating physician and/or co-PI ([name]) determines that there is a reason to significantly alter the subject's drug regimen at any time during the study, including switching to an alternate immunosuppressant. Subjects who are noncompliant with study visits or who, at any time during the study, feel that they can no longer complete the neurocognitive assessment battery may also be asked to withdraw from the study.

**13.2** Withdrawal Procedures: Every attempt will be made (phone calls, email) to connect to subjects who fail to appear at any visit or abruptly withdraw from the study. Once withdrawal is confirmed, an exit form will be completed, documenting the reason(s) for withdrawal. No attempt will be made to collect any data after withdrawal.

**13.3** Termination Procedures: Data collected from subjects who either withdraw from the study voluntarily or who are asked to withdraw will be analyzed and retained in the database.

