- Manipulative dexterity/fine motor coordination will be assessed using Grooved Pegboard Test, which involves placing 25 pegs as rapidly as possible into an equivalent number of similarly shaped holes, but varying in their orientation to the vertical. The primary dependent measure is the time it takes to complete the task.

*Quality of Life Assessment*

- Self-report measures of health-related quality of life will either be completed online using the brief, but highly reliable computer adapted tests of the NIH PROMIS system. [[www.NIHpromis.org](http://www.NIHpromis.org)] or static short forms by pencil and paper. PROMIS scales will include: Physical Health (Physical function, pain intensity, pain interference, fatigue, sleep disturbance, sleep-related impairment); Mental Health (depression, anxiety); Social Health (satisfaction with social roles). These measures, along with the SF-12, will be administered at the times of the cognitive assessment and will take 15 minutes or less to complete.

*Blood Draw*

- One 7 to 10 mL blood sample will be collected at each visit. Over the course of the study, we will collect about 6 to 9 teaspoons of blood.
- If the subject consents to the genetic portion of the study, a portion of the baseline blood draw will be used to study specific polymorphisms that are known to affect how tacrolimus metabolizes in the body. The subject may still participate in study even if they do not consent to the genetic option.

**5.3** Follow-Up: After the last study session at 12 weeks Post-BASELINE, patients who were assigned to the *Envarsus® XR* group will have the opportunity to remain on the extended-release formulation at their own expense.

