## 14.0 Risks to Participants

*For each risk or set of risks below, include the procedures to be performed to lessen the probability, magnitude, duration, or reversibility of those risks.*

**14.1** Foreseeable Risks: 1. Possible bruising as a result of needle stick to obtain blood sample; 2. CNI-immunosuppressant therapy is SOC in this population, and there are risks associated with their use (refer to attached package inserts for both immediate- and extended-release tacrolimus). All participants will be monitored by [name] throughout this study as SOC, thus there is no added risk in switching from immediate-release to extended-release tacrolimus.

**14.2** Reproduction Risks: N/A

**14.3** Risks to Others: N/A

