## **18.0 Provisions to Monitor the Data to Ensure the Safety of Participants:**

**18.1 Data Integrity Monitoring:** This study will be monitored according to GCP guidelines. The investigator will allocate time for such monitoring activities. The investigator will also ensure that the monitor or other compliance or quality assurance reviewer is given access to all the above noted study-related documents and study related facilities and has adequate space to conduct the monitoring visit. Additionally, case report forms will be periodically reviewed by the study team

**18.2 Data Safety Monitoring:** All subjects have been recruited from [name] patient population and have regularly scheduled clinic visits to assess their health post-transplant. Tacrolimus levels are taken by Fairview staff and they have a protocol in place if a critical result is found. If randomized to XR group, physicians follow on-label dosing and monitoring guidelines.

The monitoring plan will be conducted by the Principal Investigators and the Study Team. The monitoring plan will address the following: enrollment, adverse events, outcome data, protocol non-compliance, and new and relevant information to the study participants. Study coordinators will collect AEs and SAEs via EPIC and through conversation with the subjects during study visits. Study coordinators will record any AEs on CRFs and on CTSI provided AE log sheet. They will then report AEs and SAEs in a timely manner, according to GCP guidelines to the PIs and the IRB, when necessary. Unexpected SAEs are to be reported to the IRB at most 24 business hours after the event and expected AEs will be reported annually with the continuing reviews.

Additionally, subjects may be removed from the study if determination by the treating physician deems there is a reason to significantly alter the subject's drug regimen at any time during the study, including switching to an alternate immunosuppressant.

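### Section 13.2 stops all data collection at withdrawal with no exception for AEs or SAEs, so events that lead to withdrawal have no planned outcome, and 18.2 gives no end date for AE collection

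*Combined protocol and SAP*

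**What the plan says.** **Withdrawal.** Under 13.1 a subject will be asked to withdraw if the treating physician or co-PI "determines that there is a reason to significantly alter the subject's drug regimen at any time during the study"; a switch to another immunosuppressant is included. Section 18.2 repeats this as something that may happen. Under 13.2, once withdrawal is confirmed, "an exit form will be completed, documenting the reason(s) for withdrawal", and then: "No attempt will be made to collect any data after withdrawal". Under 13.3, data already collected from withdrawn subjects "will be analyzed and retained in the database".

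**Safety collection.** Section 18.2 says: "Study coordinators will collect AEs and SAEs via EPIC and through conversation with the subjects during study visits". It gives no date at which this ends and no rule for following an open event. AEs go on CRFs and an AE log, and unexpected SAEs go to the IRB on a short deadline. Sections 12.3 and 19.2 give the whole research team EPIC access, and 12.3 limits recruitment to internal patients.

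**After week 12.** XR is supplied by the sponsor (4.2). After the last session, XR patients "will have the opportunity to remain on the extended-release formulation at their own expense" (5.3). Nothing is said about those who do not, and no further contact is scheduled.

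**Risk statements.** Section 14.1 says that changing from IR to XR adds no risk, because participants are monitored during the study as standard of care. Section 9.1 requires contraception "throughout the study period and for 90 days after the final study drug administration", while 14.2 reads "Reproduction Risks: N/A".

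**The concern.** A significant change of regimen can be a response to an adverse event. Where it is, 13.1 and 13.2 together end data collection while the event may still be open. The exit form gives the reason, but no provision captures what happened next. A later SAE in the same subject has no planned route into the reporting process of 18.2.

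This matters for the trial's own question. Section 2.3 hypothesises fewer adverse cognitive and motor effects on XR, and 2.1 says that tacrolimus neurotoxicity is often reversible when exposure is reduced. Whether an event resolved after the regimen changed is therefore informative, and it is what the rule leaves out. These withdrawals are requested by the study, so the subject has not necessarily refused further use of the record.

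A weaker form of the problem arises after week 12. There the plan is silent rather than prohibitive: coordinators cannot tell from 18.2 when AE collection ends.

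**Working it through.** The point rests mainly on text, so the provisions are set side by side first. Arithmetic only bounds the size.

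**1. What is captured for a subject withdrawn because of an adverse event**

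| Item | Provision | Planned capture |
|---|---|---|
| Event up to withdrawal | 18.2, 13.3 | Yes |
| Reason for leaving | 13.2, exit form | Yes |
| Outcome of the event | 13.2 | None |
| Later SAE, up to the planned week-12 date | 13.2 against 18.2 | None under 13.2 |

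Section 18.2 puts no cut-off on EPIC review, so it could be read as continuing. But 13.2 is the specific rule for withdrawn subjects, covers data of every kind and has no safety exception. At best the two sections conflict.

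**2. Number affected by the withdrawal rule**

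Inputs: 74 enrolled and 65 completers (Study Summary, 11.1, 16.2).

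- Planned losses: 74 − 65 = 9, and 9/74 = 12.2%.
- This allowance covers every cause. Section 13.1 also lists non-compliance with visits and inability to complete the test battery. The share due to adverse events is not given, so 9 does not measure it.

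**3. Time not observed**

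- After BASELINE, a withdrawn subject loses the interval from withdrawal to the planned week-12 visit: at most 12 weeks, or 13 with the 7-day window.
- Longest current span from Pre-BASELINE to week 12: 60/7 + 12 = 20.6 weeks (21.6 with 7 days added). Section 8.0 says about 32 weeks and the Study Summary says six months. The 32 weeks fits the deleted 24-week visit: 60/7 + 24 = 32.6 weeks. Neither stated duration therefore gives a usable AE end date, and no contact fills the difference.

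**4. Formulation change after week 12**

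- XR completers: 65/2 = 32.5, so 32 or 33.
- The share who do not continue XR is not stated. Assuming anything from 0% to 100% gives 0 to about 33 subjects; 25% would be about 8.
- The 90-day contraception period is 90/7 = 12.9 weeks. For a subject who stops XR at week 12, it has no matching follow-up.

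**5. What the trial could say about added risk**

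For zero events of a given type in n subjects, the one-sided exact 95% upper bound is 1 − 0.05^(1/n).

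- n = 32: 8.9%
- n = 37 (half of 74): 7.8%

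Even complete follow-up with no events would not establish the statement in 14.1.

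**The case against.** The strongest reply is that these patients are not unobserved. Clinic visits continue (18.2), the co-PI will probably remain a treating physician (19.2), both products are on-label (4.1), and safety is not among the endpoints in 3.0. This stands as far as care is concerned: the gap is in study data. It does not answer 13.2, because information in the clinical record that nobody plans to extract does not reach the AE log or the IRB report.

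The CRF and AE log are not in the documents and may have an outcome field. That would help for events closed before withdrawal, but 13.2 still plans no attempt to complete it afterwards. Consent wording on record access is also unseen.

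Three stronger readings are tempting and are not supported:

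- *AE collection ends at week 12.* No section says so. EPIC is an AE source without a cut-off, so later capture is unspecified, not excluded.
- *The trial causes a switch from XR back to IR in up to 37 subjects.* Section 5.3 only offers continuation at own expense. A further change for the others is a reasonable presumption, but the protocol neither states it nor gives a number. The figure 37 counts randomised subjects, not completers.
- *Harm would be under-reported in one arm.* The withdrawal rule and AE sources are the same in both arms. A change after week 12 lies outside the randomised comparison, and nothing shows differential withdrawal.

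Nor does 18.2 say that coordinators take tacrolimus levels from EPIC; it names only AEs and SAEs. Finally, 9.1 against 14.2 is a separate documentation inconsistency. A contraception period does not by itself require data collection.

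**Conclusion.** The point holds for withdrawal, on explicit text. A subject asked to leave because of an adverse event passes out of safety collection by rule, although a source that needs no visit is already in use. How many subjects this concerns cannot be derived; the 9 of 74 is an all-cause allowance. The time lost after BASELINE is at most about 12 to 13 weeks per subject.

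After week 12 the finding is narrower: no AE end date, no planned contact, and no record of which formulation XR subjects then take. The range of 0 to about 33 is an assumption. Section 14.1 covers only the change from IR to XR and claims more than a trial of this size could show. The conclusion assumes that 13.2 means what it says and that no unseen document overrides it.

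**What to change.** The changes concern data collection and wording only. Clinical handling of any formulation change stays with the treating physician.

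- **13.2:** limit the stop to study testing. For subjects who have not refused record access, continue AE and SAE collection by EPIC review to the planned week-12 date. Follow events open at withdrawal to resolution or to a fixed, capped date.
- **18.2:** state the end date of AE/SAE collection for all subjects. Record by chart review which formulation each XR subject takes after study supply ends.
- **14.1:** limit the no-added-risk statement to what the study observes.
- **14.2 and 9.1:** reconcile the not-applicable entry with the 90-day contraception requirement.
- **8.0 and Study Summary:** align the stated duration with the four-visit schedule, so that the AE end date can be read from it.

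Cost: a short amendment, consent wording on continued record access, and one chart review per affected subject by existing coordinators. No visit is added.
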